Even if it can be shown that dietary NO_3^- acutely improves muscle function in older men and women, it remains to be established whether such benefits can be sustained, and/or whether such effects have a positive impact on a person’s daily life. This is not necessarily a given, as it is well known that tolerance develops quite quickly in response to *pharmacological* nitrates, e.g., glyceryl trinitrate (nitroglycerin) (49). This does not seem to be true, though, for dietary NO_3^- (50,51) – in fact, animal studies indicate that ingestion of NO_3^- for 5-7 days may lead to positive adaptations in calcium handling proteins and hence force production in muscle that would tend to mitigate age-related declines in these parameters (40). Notably, however, a recent study of humans was unable to reproduce these findings (31).

Our **Preliminary Data** suggest that the effects of dietary NO_3^- on muscle speed and power are maintained (but not enhanced) for at least 14 days with repeated (i.e., daily) dosing in humans (see below).

Preliminary data

Using methods essentially identical to those to be employed in the proposed experiments, including use of a “gold standard”, double-blind, placebo-controlled, crossover design, we previously demonstrated that dietary NO_3^- intake increased maximal knee extensor speed (Vmax) and power (Pmax) in 12 healthy, younger men and women by $11\pm 5\%$ ($P<0.05$) and $6\pm 3\%$ ($P<0.05$), respectively (37). We observed similar dietary NO_3^- -induced improvements in muscle speed and power in 13 athletes performing multi-joint, multi-muscle, i.e., sprint cycling, exercise (38). Lastly, we found even greater increases in Vmax and Pmax (of $12\pm 5\%$, $P=0.09$, and $13\pm 4\%$, $P<0.05$, respectively) in nine middle-aged patients with systolic heart failure (HF) (52). The greater beneficial effect of dietary NO_3^- in HF patients presumably reflects the fact that, similar to healthy aging, HF results in reduced NO bioavailability (53).

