2.0 Rationale and Specific Aims

We hypothesize that increased dietary NO_3^- intake will enhance muscle NO-sGC-cGMP signaling in older men and women, leading to an increase in maximal speed and power.

Helping drive our hypotheses are the consistent improvements in muscle speed and power that both we and others have observed following dietary NO_3^- intake in healthy younger study participants (37), athletes (38,39), and especially heart failure patients (52).

By focusing specifically on changes in muscle contractile properties, we will not be able to determine whether dietary NO_3^- supplementation reduces the O_2 cost of exercise in older study participant. We will also not be measuring the effect of acute and/or chronic dietary NO_3^- intake on muscle blood flow, or on muscle energetics or aerobic exercise performance. We will also not be testing whether dietary NO_3^- intake improves insulin sensitivity. In preliminary experiments, however, we have not been able to reproduce the O_2 -sparing effect of NO_3^- ingestion, and several recent studies have reported that dietary NO_3^- (or NO_2^-) does not significantly improve aerobic exercise function in older men and women (32-35). Similarly, several other recent studies have demonstrated that, contrary to the results of *in vitro* or animal experiments, dietary NO_3^- does not enhance insulin sensitivity in older humans (58-60). We therefore believe that we are well-justified in focusing on changes in muscle contractile properties, especially in light of our preliminary data and the important role that reductions in muscle function play in the aging process.

Because our focus is muscle contractile function, we considered using percutaneous electrical nerve stimulation rather than voluntary exercise. However, this approach inverts the normal orderly recruitment of motor units, preferentially depolarizing larger alpha motor neurons innervating type II muscle fibers (cf. 61 for review). Thus, while potentially magnifying the effects of dietary NO_3^- on muscle speed and power it would significantly diminish the external validity of our findings.

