Measurement of plasma NO₃⁻, NO₂⁻: Venous blood samples will be obtained prior to consumption of BRJ w/ or w/o NO₃⁻ and every hour thereafter for 3 hours, plasma rapidly separated by centrifugation, and frozen at -80° C until subsequently analyzed for NO₃⁻ and NO₂⁻ concentration using HPLC as described above.

Measurement of skeletal muscle contractile function: A Biomed 4 system will be used to measure each subject's muscle contractile properties as previously described (30,33). Briefly, study participant will perform maximal knee extensions with their dominant leg at angular velocities of 0, 1.57, 3.14, 4.71, and 6.28 rad/s. (Not all older individuals may be able to achieve the highest velocity – if not, the highest achieved angular velocity and associated torque will be used in all subsequent calculations.) The subject will perform 3-4 knee extensions at each velocity, with 2 minutes of rest allowed between each set of contractions. To eliminate artifacts, data will be "windowed" to isolate the isokinetic phase and smoothed using a 9 point weighted moving average filter using the manufacturer's software. The highest torque generated at each velocity will be used to calculate peak power at that velocity, after which the resulting power-velocity curve will be fit with a parabolic function to determine the subject's Pmax and Vmax (i.e., Y-

maximum and 2nd Y-intercept of fitted parabola, respectively) as previously described (30,33).

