Measurement of perceived fatigue, physical function, and physical activity: Perceived fatigue and physical function will be assessed using PROMIS® Short Forms 8a and 20a, respectively, which are physical functioning questionnaires. Actual physical function will be quantified by the FIT Core using a suite of tests, i.e., usual gait speed, fast gait speed, Short Physical Performance Battery, 30 s chair stand performance, 6 min walk distance. Physical activity will be quantified using ActiGraph wGT3X-BT activity monitors (ActiGraph, Pensacola, FL). On Study Day 1, each participant will be given a fully-charged monitor and directed to wear the monitor on their right hip (superior to the iliac crest) for the next 7 days, removing it only when sleeping or during aquatic activities (i.e., bathing, swimming), and to complete a log of when the monitor is worn. On day 7, they will exchange the monitor for another, to be worn for the next 7 days. Upon return of the monitors, the data will be downloaded using the ActiLife 6 software, divided into 60 second epochs, and analyzed to quantify both total and bouted (i.e., >10 min duration) sedentary behavior, light physical activity, and moderate-to-vigorous physical activity (<100 counts/min, 100-2020, and >2020 counts/min, respectively). Total counts will also be recorded, since this may be more closely associated with the health benefits of physical activity (68). Results will be considered valid only if each monitor is worn for at least 10 hours/day over at least 4 days (including at least one weekend day) each week. Subsequently, the subject will perform an “all out” 50 contraction fatigue test (at 3.14 rad/s) to determine whether dietary NO₃- influences fatigue resistance (i.e., increases average power) during repetitive, maximal activation. Finally, recovery of muscle function will be quantified by measuring restoration of torque during knee extensions performed periodically over the next 10 min.

Risks

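### Fatigue resistance is equated with average power over 50 contractions, so a rise in starting power alone can register as better fatigue resistance

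*Combined protocol and SAP*

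**What the plan says.** The fatigue test is described in Section 5.0 (Study Methods), in the paragraph on perceived fatigue, physical function and physical activity. It is a maximal "50 contraction fatigue test (at 3.14 rad/s"), carried out to learn whether nitrate "influences fatigue resistance (i.e., increases average power) during repetitive, maximal activation". The parenthesis makes average power the definition of fatigue resistance. No percent decline, slope, end-to-start ratio or adjustment for starting power appears in the available text.

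Section 8.0 names Vmax, Pmax and muscle cGMP as primary outcomes and describes no analysis for this test. No aim in Section 2.0 mentions it by name. The hypothesis in Section 2.0 is that nitrate strengthens muscle signalling, "leading to an increase in maximal speed and power".

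**The concern.** Fatigue resistance concerns how well output is held during repeated effort. Average power also depends on how high output was at the start, and the treatment is expected to raise that. The crossover does not remove the problem: if nitrate works as hypothesised, the same person starts at different power under the two treatments.

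A gain in unfatigued power could therefore be counted a second time, as a gain in fatigue resistance. A modest loss of fatigue resistance could be hidden by a higher start.

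**Working it through.** The plan gives no figure for this test, so there is nothing to reproduce. The check is how much average power moves when the fatigue profile stays fixed.

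**Inputs from the documents**
- Test velocity: 3.14 rad/s (Section 5.0).
- Gains in healthy younger adults: Pmax +6%, Vmax +11% (Section 1.0, Preliminary data).
- Gains in heart-failure patients: Pmax +13%, Vmax +12% (same place). The Vmax gain there is reported with P=0.09.
- Power-velocity curve: a parabola with Pmax at its peak and Vmax at its second intercept (Section 5.0).

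**Assumptions**
- Baseline Vmax is not in the available text; 6.28 to 10 rad/s is tried.
- The parabola passes through zero power at zero velocity.
- Where a decline is needed, power falls by F = 50% over the test on placebo, either linearly or exponentially (time constant 20 contractions). The documents give no value for F.

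**Step 1: the identity.** Average power = P0 × m, where P0 is starting power at 3.14 rad/s and m is the mean fraction of it maintained. If m is unchanged, average power changes by exactly the same percentage as P0, whatever the depth or shape of the decline. Average power divided by P0 changes by 0%.

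**Step 2: how far P0 moves.** The test runs at one fixed velocity, so a Pmax gain does not carry over directly. With P(v) = 4 × Pmax × x × (1 − x) and x = v/Vmax, a gain gP in Pmax and gV in Vmax multiplies P0 by (1 + gP) × x′(1 − x′) / [x(1 − x)], where x′ = x/(1 + gV).

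| Gains | Baseline Vmax (rad/s) | x | x′ | x′(1−x′)/[x(1−x)] | Change in P0 |
|---|---|---|---|---|---|
| Younger | 6.28 | 0.5000 | 0.4505 | 0.9902 | 1.06 × 0.9902 = 1.050, +5.0% |
| Younger | 7 | 0.4486 | 0.4041 | 0.9735 | 1.06 × 0.9735 = 1.032, +3.2% |
| Younger | 8 | 0.3925 | 0.3536 | 0.9586 | 1.06 × 0.9586 = 1.016, +1.6% |
| Younger | 10 | 0.3140 | 0.2829 | 0.9418 | 1.06 × 0.9418 = 0.998, about 0% |
| Heart failure | 6.28 | 0.5000 | 0.4464 | 0.9885 | 1.13 × 0.9885 = 1.117, +11.7% |
| Heart failure | 8 | 0.3925 | 0.3504 | 0.9547 | 1.13 × 0.9547 = 1.079, +7.9% |

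Below 6.28 rad/s the change is larger. Section 5.0 allows for that region: "Not all older individuals may be able to achieve the highest velocity", which is 6.28 rad/s.

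**Step 3: how much worsening can be hidden.** With a linear decline, m = 1 − F/2, so placebo m = 0.75. Average power under nitrate stays above placebo until the end-to-start ratio falls to 1.5/(1 + gain) − 1:
- gain 1.6%: 1.5/1.016 − 1 = 0.476, so F can reach 52.4%
- gain 5.0%: 1.5/1.050 − 1 = 0.429, so F can reach 57.1%
- gain 7.9%: 1.5/1.079 − 1 = 0.390, so F can reach 61.0%
- gain 11.7%: 1.5/1.117 − 1 = 0.343, so F can reach 65.7%

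With the exponential decline, mean loss is 0.6825 × F, so placebo m = 1 − 0.6825 × 0.50 = 0.6588. Break-even F = (1 − 0.6588/(1 + gain))/0.6825, which gives 51.5%, 54.6%, 57.1% and 60.1% for the same four gains.

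**Step 4: one worked case.** Take a linear decline that worsens from 50% to 53%. The relative measure falls from 0.750 to 0.735, or −2%. With a 5.0% gain in P0, average power is 1.050 × 0.735/0.750 = 1.029, a rise of 2.9%. With a 1.6% gain it is 1.016 × 0.735/0.750 = 0.996, a fall of 0.4%, so at that size the worsening would no longer be hidden.

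**The case against.** The strongest objection is about size. It is tempting to infer that average power must rise by the full 6% or 13% Pmax gain. The documents do not support that. The test velocity is fixed, and a rise in Vmax shifts the peak of the curve towards higher velocities. With the younger-adult gains and a baseline Vmax near 10 rad/s, the inflation disappears. The 13% comes from nine heart-failure patients, a condition excluded in Section 3.0. This objection stands, and it is why the size is given as a range.

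A reader might also infer from the slow-to-fast analogy in Section 1.0 that nitrate would speed fatigue and that the measure would then reverse the truth. The text offers the analogy as a euphemism that holds only qualitatively, and no available passage reports or predicts faster fatigue. Nor does the recovery measure share the flaw on the text: whether restored torque will be expressed in absolute or relative terms is simply unspecified. Neither argument is relied on here.

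It is also fair to say that sustained absolute power is a worthwhile outcome in older adults, and that the 50 contractions would allow a relative index to be computed anyway. So the question is not beyond reach of the data. A ratio is not neutral either: higher initial output with the same final output scores as worse, and pacing affects it. This argues for reporting both measures. It does not rescue the present definition, which gives one quantity the name of another.

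**Conclusion.** The point holds for the definition. It rests on an identity and on the trial's own hypothesis, not on any assumed rate of decline. As written, the test can show improved fatigue resistance when the relative decline is unchanged or modestly worse.

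The size is uncertain. For an unchanged relative decline, the spurious gain is about 0% to 5% with the younger-adult gains (assumed baseline Vmax from 10 down to 6.28 rad/s), and about 8% to 12% with the heart-failure gains (8 down to 6.28). These figures depend on the assumed Vmax, on the parabola, and on gains borrowed from other populations. The older-adult pilot results for Pmax and Vmax are in a figure that could not be seen.

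A reader might infer that the trial's main findings are compromised. They are not: the fatigue test is outside the primary outcomes, and nothing here touches Vmax, Pmax or cGMP. This is a low-cost correction to a supporting measure.

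**What to change.** In Section 5.0, delete the parenthesis that equates fatigue resistance with increased average power. Define fatigue resistance by a relative index from the same 50 contractions. Two examples are mean power of the last 10 divided by mean power of the first (or best) 10, and average power divided by peak power in that test. Choose one index before unblinding. Report average power or total work alongside it, under its own name, and state that the two will be read together.

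The cost is a sentence or two of protocol text and a different calculation on the same contractions, with no added visits, procedures or participants. The downside is that a ratio is noisier than average power and itself depends on starting power and pacing, which is the reason to keep both.

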7.0 Study Withdrawal/Discontinuation

A participant may withdrawal from the study at any time verbally or by providing this request in writing as described in the informed consent document. As outlined in the consent document, if the participant/patient wishes to withdraw consent, the PI will:

- no longer use and take reasonable steps to destroy all blood/tissue samples and information
- not take back any research / analyses already completed

A potentially more important limitation to this research is the lack of pilot data for certain measurements. Thus, although we will have adequate power to detect increases in Vmax and Pmax), we cannot be assured that we will be able to detect differences in all of our endpoints. However, the proposed experiments would still provide the data needed to design a larger study that is adequately powered to detect changes in all variables.

9.0 Privacy/Confidentiality Issues

All study activities will be performed within areas respective of the participants' right to privacy.

Although there can be no absolute guarantee of confidentiality, every practical precaution will be taken.

Each study participant will be assigned a unique ID. Samples and information will be de-identified using this unique ID.

10.0 Follow-up and Record Retention

Study recruitment will be ongoing. The duration of the entire study is expected to be 24 months.

Any remaining blood samples will be de-identified and discarded. The de-identified data will be retained on computer files indefinitely. Hard copy study documents will be kept in a locked, file cabinet in a locked room. Electronic study information will be stored on a

specified, password-protected network that is backed up daily. Only the study team and the relevant personnel will have access. Files will be kept on site until 2 years after study completion, and then sent to a secure archiving facility. Files will be kept for 7 years after study completion per state law requirements.

